## 1. Purpose and aims

There is a clear rationale for developing interventions targeting negative symptoms of schizophrenia as negative symptoms are a stronger indicator of current and future functioning than positive symptoms (Velligan et al., 2015) and because they respond poorly to medication (Veerman et al., 2017) and existing psychological interventions (Fusar-Poli et al., 2015). This is reflected in the National Institute of Mental Health (NIMH)- Measurement and Treatment Research to Improve Cognition in Schizophrenia (MATRICS) consensus statement (Kirkpatrick, Fenton, Carpenter, & Marder, 2006) that emphasised that persistent negative symptoms represent an unmet therapeutic need for patients suffering from schizophrenia.

The purpose of this study is to evaluate, in a scientific manner, the intervention developed by Swanson et al. 2021: Metacognitive Training (MCT) Minus. This intervention adapted MCT to target negative symptoms in psychotic disorders (e.g. schizophrenia, schizoaffective or non-affective functional psychosis) as the original version of MCT (Moritz & Woodward, 2007) focused exclusively on positive symptoms. The specific aim is to study whether MCT Minus is a promising treatment for the intended population in terms of:

- Reductions in negative symptoms as measured by the Clinical Assessment Interview for Negative Symptoms (CAINS) (Forbes et al., 2011), the Motivation and Pleasure Scale- Self-Report (MAP-SR) (Llerena et al., 2013) and the Positive and Negative Syndrome Scale (PANSS) (Kay et al., 1987)
- Reductions in severity of defeatist attitudes as measured by the Dysfunctional Attitudes Scale (DAS) (Weissman & Beck, 1978)
- Improvements in reflective ability as measured by the Reflective Functioning Questionnaire (RFQ-8) (Fonagy et al., 2016)
- Reduction in internalised stigma as measured by the Internalized Stigma of Mental Illness Scale-9 (ISMI-9) (Hammer & Toland, 2017)
- Reductions in depression as measured by the Calgary Depression Scale for Schizophrenia (CDSS) (Addington, Addington, & Schissel, 1990)
- Improved functioning as measured by the World Health Organization (WHO) Disability Assessment Schedule (WHODAS) 2.0 (WHO, 2010)

The research will add to existing research by identifying and measuring potential mechanisms of change for negative symptoms (i.e., defeatist attitudes, reflective functioning, stigma and depression). It will also add to the existing evidence base by measuring whether the cognitive biases addressed in MCT lead to changes in the wider conceptualisation of metacognition used elsewhere and whether the promising results seen in the feasibility study of MCT Minus (Swanson et al., 2021) can be replicated in a randomised controlled trial (RCT) with a control group and a blinded assessor. We also hope to replicate the findings of a previous study by Shan et al. 2020, where MCT was found to be related to the modulation of default-mode network (DMN) homogeneity in schizophrenia, an area thought to be involved in self- and other-reflectivity.

## 2. State-of-the-art: Introduction

While clinicians tend to focus on positive symptoms as primary treatment targets in schizophrenia, patients prioritize the treatment of depressive and negative symptoms (Moritz et al., 2017). Persistent negative symptoms are experienced by approximately 20%–40% of individuals diagnosed with schizophrenia (Sarkar et al., 2015). Current research indicates that negative symptoms are independent from positive symptoms, depression, cognitive dysfunctions, and disorganization (Galderisi et al., 2018). However, neither medication nor existing psychosocial interventions have proven to be efficacious in reducing negative symptoms (e.g., Correll & Schooler, 2020; Fusar-Poli et al., 2014; Veerman et al., 2017). Consequently, Lutgens et al. (2017) highlighted the need for better understanding of treatment mechanisms underpinning psychological interventions that directly target negative symptoms.

Psychological conceptualizations suggest that negative symptom expression can, in some cases, be understood as a response to adverse experiences (Aleman et al., 2017). For example, Beck et al.'s (2009) cognitive model suggests that negative symptoms emerge from a process where individuals adopt coping strategies of 'shutting down' the cognitive–affective experience. This allows individuals to cope with overwhelming or aversive situations in the short term but leads to a reliance on negative symptoms (including social withdrawal, avolition, and diminished expression) to reduce exposure to, and impact of, negative experiences in the longer term. From an attachment framework, Griffiths and McLeod (2019) suggest that negative symptoms may be seen 'as responses involving emotional and social withdrawal that emerge from threats to self-security' (p. 62). If negative symptoms can be understood within cognitive and developmental frameworks, it may be possible to develop theoretically driven interventions for their treatment.

### 2.1. A cognitive model of negative symptoms

Negative symptoms are associated with low expectations of future success (Cox et al., 2016), asocial beliefs (Grant & Beck, 2009), a reduced sense of self-efficacy (Bentall et al., 2010), negative self-concepts (Lincoln et al., 2011), defeatist performance beliefs (Campellone et al., 2016) and self-stigma (Horsseleberg et al., 2016). The cognitive model therefore proposes that negative symptoms might be caused and maintained by dysfunctional beliefs arising as a consequence of repeated failures and setbacks. These appraisals might include negative beliefs about social affiliations; low expectations of pleasure, success and acceptance; defeatist beliefs about performance; and a perception of limited resources (see Beck et al., 2019). The self-perception, and perceived self-efficacy, of individuals diagnosed with schizophrenia may also be influenced by self-stigmatizing views of their mental illness. It might be that these factors result in hypervigilance to perceived criticism (Rector et al., 2005). Longitudinal studies have shown support for the cognitive model as defeatist performance attitudes and asocial beliefs are found to predict future negative symptoms (Granholm et al., 2018; Luther et al., 2015; Thomas et al., 2017).

### 2.2. Metacognition and psychosis

Metacognition was initially referred to as the capacity to think about and monitor one's mental processes (Flavell, 1979). However, the definition has broadened in contemporary research (Moritz & Lysaker, 2018), ranging 'from discrete processes involving noticing specific thoughts and feelings to more synthetic acts in which information is integrated into complex representations of the self and others' (García-Mieres et al., 2020, p. 170). This has given rise to interventions targeting metacognitive processes, some of which have been specifically developed for psychosis (e.g., metacognitive training (MCT), Moritz & Woodward, 2007; metacognitive reflection and insight therapy (MERIT), Lysaker & Klion, 2017) while others have been modified for this population (see Lysaker, Gagen, et al., 2020; Moritz et al., 2019;

Weijers et al., 2020). MCT is based on the premise that cognitive biases play a role in the development and maintenance of psychotic symptoms which can be alleviated by targeting underlying cognitive processes (Pos et al., 2018). The aims are to gain insight and to learn practical strategies to manage distressing symptoms (Schneider & Andreou, 2014). MCT has been shown to reduce delusions (Liu et al., 2018) and positive symptoms (Philipp et al., 2019) and improve cognitive insight (Birulés et al., 2020) and biases (Sauvé et al., 2020). Preliminary evidence also suggests effects on quality of life (Moritz, Andreou, et al., 2014) and illness insight (Lopez-Morinigo et al., 2020).

Several authors highlight the links between negative symptoms and compromised capacity for self/others mental state processing (Griffiths & McLeod, 2019; Gumley et al., 2014; Harder, 2014). There is evidence that suggests a link between metacognition and negative symptoms as limitations in complex metacognitive processes predict negative symptoms in first episode psychosis (Austin et al., 2019) and in more chronic samples, even after controlling for defeatist beliefs, affect recognition and neurocognitive functioning (Lysaker et al., 2015). Metacognitive deficits are also associated with concurrent and future negative symptoms when controlling for verbal memory and education (Faith et al., 2020; Lysaker, et al., 2020). Interestingly, self-reflection in itself has been found to mediate the relationship between neurocognition and negative symptoms (especially for deficits in capacity to communicate about internal states, so called diminished expression) while interpersonal cognitive differentiation (i.e., the ability to construe one's experiences as either similar or different from others' experiences) has been found to mediate the pathway between self-reflectivity and negative symptoms (García-Mieres et al., 2019, 2020). This suggests that negative symptom reduction may at least partially depend on improved metacognitive capacity and that a metacognitive intervention specifically targeting negative symptoms may be beneficial.

Swanson et al. (2021) therefore adapted MCT for negative symptoms to assess the acceptability and feasibility of the intervention, examine variable change over the course of the intervention and carry out a preliminary investigation of putative mechanisms of change. The current project is a further evaluation of this, where we hope to achieve similarly encouraging results in a randomised controlled trial (RCT) with a control group and blinding. We also hope to replicate the findings of a previous study by Shan et al. 2020, where MCT was found to be related to the modulation of default-mode network (DMN) homogeneity in schizophrenia, an area thought to be involved in self- and other-reflectivity. Importantly, it was found that high network homogeneity levels at baseline in the bilateral superior medial prefrontal cortex could predict symptomatic improvement after 8 weeks of drug plus psychotherapy treatment; this illustrates that a more developed understanding of the biological mechanisms underlying negative symptoms would allow us to identify patients that would benefit from each type of treatment and, through that, change the prognosis and treatment outcomes of the condition.

### **3. Significance and scientific novelty**

Research funding would facilitate a RCT to evaluate the intervention trialled by Swanson et al, 2021 in a more rigorous and scientific manner. Given our limited understanding of negative symptoms and how to treat them (see Galderisi et al., 2021), the study would be of both significance and scientific novelty. To fully understand the biological mechanisms behind negative symptoms is essential to be able to develop future treatment options and to identify patients that would benefit from each type of treatment. A more thorough understanding of schizophrenia would decrease the heterogeneity of the condition which would have vast implications for how individuals diagnosed with schizophrenia are treated both in society and in the healthcare setting.

#### **4. Previous results**

Two articles (which were based on the main researcher's doctoral thesis at Edinburgh University with funding from National Health Service (NHS) Lothian) have been published in Clinical Psychology and Psychotherapy (Swanson et al., 2022; Swanson et al. 2022) and a poster has been presented at "The 2022 Congress of the Schizophrenia International, Research Society (SIRS)" (6-10 April 2022 in Florence). The project will also be covered in several articles in "Empati" which is the Schizophrenia Association's paper for members which is also distributed to politicians on local, regional and national level.

#### **5. Project description**

##### **5.1. Participants, sample size, settings and ethics**

Eligible participants will be over the age of 18 with a diagnosis of schizophrenia, delusional disorder or non-affective psychosis in Region Sörmland, Region Västmanland and Region Uppland. Exclusion criteria will be evidence of severe organic brain dysfunction or a learning disability, difficulty with the Swedish language, visual and/or hearing impairment, or being unable or unwilling to provide written informed consent. Clinical teams will be approached by [name] or a research assistant and asked to inform suitable patients about the study. The research assistant will then meet the subjects and inform them (both orally and written) prior to gaining written consent. Subjects who have been allocated to the control group (i.e. supportive counselling) will be offered metacognitive training after the trial has finished if they request this. We have used t/z-test, with a power of 0,85, and a significance level of 0,05, to calculate sample size. In order to find a difference of 4 units on CAINS (as a change in total score of 4 points has been found to show a true change at a 95% confidence level in previous research (Laraki et al., 2022)), 41 participants in each arm will be needed. We will aim to recruit 45 in each arm to allow for drop-out, group heterogeneity and to make future analysis (e.g. on the effect of medication) possible. Ethical approval will be applied for at the Etikprövningsmyndigheten.

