#### **5.4. Procedure**

Written informed consent, relevant demographic information and baseline measures will be completed before beginning the intervention. The Motivation and Pleasure Scale—Self-Report (MAP-SR) (Llerena et al., 2013) will be used to certify that some level of negative symptoms exist prior to the intervention. The patients will be randomised to either MCT Minus and treatment as usual or supportive counselling combined with treatment as usual using an online calculator. Pre-, post-, and follow-up assessments will be conducted by a research assistant who is blind to group allocation. Exit interviews will be held after completing the intervention where a standardized interview schedule (with open-ended questions) will be applied to minimize variations in questions asked while retaining enough flexibility to assess individual experiences (Patton, 1987). The head of the division psychiatry in the regional health board (Region Sörmland) has approved the study and there are structures (e.g. funding, research time, support from clinicians and managers) that would facilitate recruitment and feasibility.

During the pre and post assessment visits, the patients will also undergo a magnetic resonance imaging (MRI) investigation, including anatomical (T1-weighted) imaging, resting-state functional MRI to assess changes in default mode network connectivity after the active compared to control intervention, and additionally diffusion weighted imaging (DWI) and MR spectroscopy (MRS) to relate the functional connectivity findings to structural connectivity and prefrontal glutamate levels.

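### Does resting the 4-point CAINS target on a true-change threshold call for a change to the sample size section?

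*Protocol*

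**What the plan says.** Section 5.1 states the method as "t/z-test, with a power of 0,85, and a significance level of 0,05". The target is worded "In order to find a difference of 4 units on CAINS (as a change in total score of 4 points has been found", and the reason continues "to show a true change at a 95% confidence level in previous research". The result is 41 participants in each arm, raised to 45 partly to cover drop-out. Neither the SD nor the sidedness of the test is given.

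Section 5.4 sets the comparison: patients are "randomised to either MCT Minus and treatment as usual or supportive counselling combined with treatment as usual". Section 1 asks whether the promising feasibility results "can be replicated in a randomised controlled trial (RCT) with a control group and a blinded assessor", but gives no numbers from that study. Section 2 says that "neither medication nor existing psychosocial interventions have proven to be efficacious in reducing negative symptoms", again without a between-arm figure. Section 6.1 plans a repeated measures ANCOVA over the pre, post and follow-up assessments.

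**The concern.** A threshold for true change answers a measurement question: is an observed shift in a score larger than error? The target in a two-arm sample size answers another: how large a difference between arm means is worth detecting, or can be expected? Section 5.1 uses the first to justify the second. The comparator is supportive counselling on top of usual treatment, so change within the MCT Minus arm is not the quantity under test.

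The target also drives the sample size. With the protocol's other inputs held fixed, a move from 4 points to 3 raises the requirement from 41 to 73 per arm. If a 3-point advantage over counselling mattered, the quoted 85% might not describe the trial's chance of finding it, and a null result would be hard to read.

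**Working it through.** **Inputs.** From section 5.1: difference 4 points, power 0.85, significance level 0.05, 41 per arm, 45 to be recruited. Not stated: SD, sidedness, drop-out rate. The difference is read as between arms because the numbers are given per arm.

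**Step 1: is 41 coherent?** Without an SD, 41 cannot be derived forward, so solve for the standardised difference d with the normal approximation:

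d = (z for alpha + z for power) × sqrt(2/n), and SD = 4/d.

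- Two-sided: (1.960 + 1.036) × sqrt(2/41) = 2.996 × 0.2209 = 0.662, so SD = 4/0.662 = 6.04.
- One-sided: (1.645 + 1.036) × 0.2209 = 0.592, so SD = 4/0.592 = 6.75.

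The noncentral t gives 0.670 (SD 5.97) two-sided and 0.597 (SD 6.70) one-sided. As a forward check by the normal formula with SD 6: 2 × 2.996² × 6²/4² = 40.4, which rounds up to 41. The stated number is coherent with an SD of about 6.

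**Step 2: how much rests on the 4?** Noncentral t with the implied SD and 85% power: 27 per arm for 5 points, 41 for 4, 73 for 3. The same three numbers result one-sided and two-sided.

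**Step 3: what do the planned numbers detect?** Two-sided, SD 5.97, noncentral t. The adjusted rows assume that 5.97 is a raw-score SD and that the ANCOVA uses baseline CAINS. The residual SD is then 5.97 × sqrt(1 − r²): 5.17 at r = 0.5 and 4.26 at r = 0.7. Both correlations are assumed.

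| Analysis | 4 points, 41 / 45 evaluable per arm | 3 points, 41 / 45 evaluable per arm |
|---|---|---|
| Unadjusted | 85% / 88% | 61% / 65% |
| Adjusted, r = 0.5 | 93% / 95% | 74% / 78% |
| Adjusted, r = 0.7 | 99% / 99% | 88% / 91% |

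At 2 points, unadjusted, power is 32% / 35%. If the SD behind 41 is already that of a change score or a residual, only the unadjusted row applies.

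**Step 4: the margin for drop-out.** Recruiting 45 leaves 41 after a loss of 4, and 4/45 = 8.9%. The columns for 45 assume no loss.

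**Step 5: does the document hold a better target?** Sections 1 and 2 give no between-arm figure in either direction. If the section 2 statement means that little change is expected on counselling, a 4-point change on MCT Minus would be close to a 4-point difference between arms. The text therefore does not show that 4 is too large or too small.

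**The case for a change.** The strongest case for a change is that the protocol itself fixes the target and its reason, so this is not detail deferred to a statistical analysis plan. The reason does not support the figure, the figure sets the sample size, and the remedy is two or three sentences at no cost in patients, visits or measures. It would define the target as a between-arm difference, say whether 4 is the smallest worthwhile or the expected advantage, and give the SD and sidedness.

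The logical core stands: a true-change threshold does not by itself justify a between-arm difference, and nothing else in the protocol does. The stated consequences stand less well.

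- Section 5.1 never calls 4 points worthwhile or expected against counselling. That a reader will take it so is a guess.
- Power below 4 points need not fall under 85%. At 3 points it is 88% with 41 evaluable per arm if r = 0.7 and the implied SD is a raw-score SD.
- One can rescale the threshold to 4 × sqrt(2/41) = 0.88 points for a difference of two mean changes. That assumes a one-patient threshold and independent errors, neither of which is stated, and 0.88 is only rescaled measurement noise. It says nothing against a target of 4.
- Requiring a mean difference no smaller than a reliably detectable change is an imperfect anchor, but a recognisable one.

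**Conclusion.** No change to the plan follows, because nothing would be gained in its figures or analysis. The rationale in section 5.1 is thin. Even so, 41 per arm is consistent with 85% power at 4 points for an SD of about 6.0 two-sided or 6.7 one-sided, equivalent to 0.67 or 0.60 SD by the noncentral t. No alternative target can be drawn from the document, and recruitment would stay at 45 per arm. The missing SD, sidedness and sensitivity range are supporting detail that a statistical analysis plan may hold. Spelling out the ground for 4 points would help a reader but would leave every stated number, test and conclusion as it is.

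This rests on the SD being the back-solved value and on taking the protocol's account of the threshold at face value, since the cited measurement study is not at hand. When results are read, a null finding should be taken as evidence about a difference of around 4 points. It should not be taken as showing that smaller advantages are absent or unimportant.

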##### **5.2. Intervention**

The original MCT intervention was adapted to negative symptoms by incorporating psychoeducation and strategies to target the cognitions suggested by the cognitive model (Beck et al., 2009) to be implicated in the development and/or maintenance of negative symptoms (see Table 1). Although some of the strategies have traditionally been used to target positive symptoms, it is assumed that the same reasoning styles lead to negative symptoms through the dysfunctional cognitions discussed previously (e.g., jumping to conclusions in regard to social rejection and a dysfunctional attribution style reinforcing social withdrawal). Metacognitive training for negative symptoms consists of eight sessions, delivered individually as there is evidence indicating that this approach may lead to stronger effect sizes than delivery in a group format (Liu et al., 2018). The developer of MCT ([name]) approved the modification.

##### **5.3. Outcome measures**

This study will use a combination of interviews and self-rated questionnaires to assess negative symptoms. The primary outcome measures will be the Clinical Assessment Interview for Negative Symptoms (CAINS) (Forbes et al., 2011), the Motivation and Pleasure Scale—Self-Report (MAP-SR) (Llerena et al., 2013), and the Positive and Negative Syndrome Scale (PANSS) (Kay et al., 1987) (with the PANSS negative factor proposed by Wallwork et al. (2012)). The CAINS was chosen as it has been developed to measure negative symptoms as defined by the NIMH consensus development conference (i.e., blunted affect, alogia, anhedonia, asociality and avolition) (Kumari et al., 2017). (We replaced the Brief

Negative Symptom Scale (BNSS) (Kirkpatrick et al., 2010) with CAINS as the BNSS has not been validated or translated into Swedish).

To identify and measure mechanisms of change, four measures will be used: the Dysfunctional Attitudes Scale (DAS) (Weissman & Beck, 1978) to measure the severity of defeatist attitudes; the Reflective Functioning Questionnaire (RFQ-8) (Fonagy et al., 2016) to assess metacognitive capacity; the Calgary Depression Scale for Schizophrenia (CDSS) (Addington et al., 1990) to measure depression; and the Internalized Stigma of Mental Illness Scale-9 (ISMI-9) (Hammer & Toland, 2017) to measure stigma. Finally, the World Health Organization (WHO) Disability Assessment Schedule (WHODAS) 2.0 (WHO, 2010) will be used as this has been suggested to be a more reliable measure than the Global Assessment of Functioning (GAF) (American Psychiatric Association (APA), 1987) for assessing a person's overall functioning (Gspandl et al., 2018).

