### **6. Data analysis and statistics**

#### **6.1. Quantitative data**

Repeated measures ANCOVA will be used to evaluate changes at pre, post and follow-up analysis due to the repeated-measure nature of the data whilst regression analysis will be used for identifying and measuring potential mechanisms of change for negative symptoms. Missing data on questionnaires will be replaced with case-mean substitution if fewer than 20% of the items were missing as this has been found to be a robust way of handling data missing on an item level (Fox-Wasylyshyn & El-Masri, 2005).

Preprocessing and analysis of fMRI data will be performed in the conn toolbox in Matlab, preprocessing of DWI and MRS data in FSL and LCModel, respectively, or equivalent software.

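### Section 5.3 names three unranked primary outcomes, while the 0.05, 0.85 and 41 per arm in 5.1 are tied to a single CAINS comparison

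*Protocol*

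**What the plan says.** Protocol section 5.3 opens its list with "The primary outcome measures will be the Clinical Assessment Interview for Negative Symptoms (CAINS" and continues in the same sentence with MAP-SR and PANSS (negative factor). The label is plural and no order is given. Of the three, only CAINS gets a specific reason: "The CAINS was chosen as it has been developed to measure negative symptoms as defined by the NIMH consensus development conference".

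Section 1 puts the same three scales in one aim, which starts "Reductions in negative symptoms as measured by the Clinical Assessment Interview for Negative Symptoms (CAINS". It too gives no order.

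The sample size is in section 5.1: "We have used t/z-test, with a power of 0,85, and a significance level of 0,05, to calculate sample size". The target follows: "In order to find a difference of 4 units on CAINS", justified by earlier research on "a change in total score of 4 points". The result is 41 per arm, with 45 to be recruited. No target difference is given for MAP-SR or PANSS, and no SD for any of the three.

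Section 6.1 gives the analysis: "Repeated measures ANCOVA will be used to evaluate changes at pre, post and follow-up analysis". It names neither a lead outcome nor a lead time point.

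**The concern.** Which outcomes are primary, and what the sample size rests on, are both fixed in this protocol, and they do not match. Section 5.1 describes one test on one scale. Section 5.3 announces three primary outcomes of equal standing. The trial's primary claim could therefore be CAINS alone, any of the three, or all three, and each has its own error rate and power. Only the first keeps both 0.05 and 0.85 as stated.

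The practical risk lies in reporting. As the text stands, a significant MAP-SR result alone could be presented as a positive primary outcome, in a trial sized for a difference on the CAINS interview. The scales are not interchangeable: MAP-SR is patient self-report, and section 5.4 also uses it to confirm negative symptoms at entry.

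**Working it through.** **Inputs from the protocol.** Difference 4 CAINS points, significance level 0.05, power 0.85, t/z-test, 41 per arm, 45 recruited (all section 5.1); three primary outcomes (section 5.3).

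**Assumptions, because the protocol is silent.** Two-sided tests; SD back-solved from the 41; for rules involving all three outcomes, the same standardised effect on each unless noted. Correlations between outcomes, and between baseline and outcome, are shown as ranges.

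**1. The plan's own figure.** The 41 cannot be reproduced independently without an SD, so I solve for the SD.
- By z: n = 2(1.960 + 1.036)² × (SD/4)². SD = 6 gives 40.4, rounded up to 41. The largest SD that still gives 41 is 6.04.
- By t: 41 per arm and power 0.85 need a standardised effect of 0.670, so SD = 4/0.670 = 5.97.

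So 41 fits one two-sided CAINS test at the full 0.05 with SD of about 6 and no allowance for further primary outcomes.

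**2. Success on any one of three, each at 0.05.** If independent, the false-positive chance is 1 − 0.95³ = 0.143. Simulation of correlated t statistics (400,000 draws, df 80) gives:

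| Correlation between outcomes | False-positive chance |
|---|---|
| 0 | 0.142 |
| 0.5 | 0.126 |
| 0.7 | 0.110 |
| 0.9 | 0.084 |

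These values do not depend on the SD.

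**3. 0.05 split three ways (0.05/3 = 0.0167).** At 41 per arm the noncentrality is 0.670 × √(41/2) = 3.03.
- CAINS power: the critical t (df 80) rises from 1.99 to 2.45, and power falls from 0.85 to 0.72. At 45 per arm it is 0.77. For 0.85, 54 per arm are needed.
- Baseline adjustment: dividing the noncentrality by √(1 − ρ²), with df 79, gives CAINS power 0.77 at ρ = 0.3 (noncentrality 3.18) and 0.85 at ρ = 0.5 (noncentrality 3.50). This holds only if the SD of about 6 is unadjusted.
- At least one outcome significant, no adjustment, 41 per arm: 0.98, 0.91 and 0.84 at outcome correlations 0, 0.5 and 0.8 if all three effects are equal; about 0.73 if only CAINS responds.

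**4. All three must succeed at 0.05, equal effects, no covariate gain.** If independent, joint power is 0.85³ = 0.614. Simulation gives 0.61, 0.69 and 0.75 at outcome correlations 0, 0.5 and 0.8.

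**The case against.** The strongest reply is that the two sections are compatible. Section 5.1 plainly attaches 0.05, 0.85 and 41 to CAINS, so a reader who infers that these figures belong to no stated comparison goes too far. If CAINS is tested first, both figures hold. A testing order is commonly left to the SAP, which is not at hand, so the absence of a multiplicity procedure here is no finding. All of that stands. It does not settle the ranking: 5.3 still gives three scales the same primary label, and sizing on one of them does not make it the lead.

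A second reply is that power is not necessarily lost. Under a three-way split with equal effects, the chance of winning on at least one outcome is at or within 0.01 of the target, and a baseline correlation of about 0.5 would bring CAINS itself back to 0.85. This also stands, on its conditions. The protocol gives neither the effects on the other two scales nor the covariate gain, and neither argument lowers the false-positive chance of the unadjusted any-one reading.

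Third, the 14% needs independent outcomes, whereas section 1 presents all three as measures of negative symptoms. The correlated values, 8% to 13%, are the more plausible part of the range.

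Finally, the aim is modest: "The specific aim is to study whether MCT Minus is a promising treatment for the intended population". That limits the weight of the point, but 5.1 still states a formal error rate and power.

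**Conclusion.** The point holds as a mismatch between outcome designation and sample-size basis, and should be fixed. Three unranked primary outcomes are named, and the design figures cover one of them.

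The size of the consequence depends on a success rule that the protocol does not state. The inflated error under the any-one reading needs no SD. The power figures are less firm: they rest on two-sided testing and the back-solved SD, and those involving more than CAINS also rest on assumed effects for MAP-SR and PANSS.

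A reader might infer that the protocol plans to claim success on any one scale, or that the trial is underpowered. The text supports neither. It leaves the first open without saying it, and for CAINS as sole or first-tested primary outcome the stated 0.85 at 41 per arm stands on the implied SD.

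**What to change.** In section 5.3, state that the primary outcome is the CAINS total score at one time point, post or follow-up, which the sponsor fixes before data are seen. The time point is needed because 6.1 analyses several assessments and 5.1 sized a single comparison. State also that MAP-SR and the PANSS negative factor are secondary or, if confirmatory claims on them are wanted, that they are tested only after CAINS is significant, in an order fixed in advance. CAINS is the natural choice: it is the only outcome used for sizing and the only one of the three with a specific reason given.

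If the sponsor prefers to keep three primary outcomes, the protocol should state the success rule, and 5.1 should restate the power under that rule with the assumed SD and covariate gain.

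Cost: a short text change in 5.3, and in the registration if it lists the same three outcomes. No extra patients or assessments are needed. The downside is that MAP-SR or PANSS alone could no longer make the trial positive.
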